1.2 Secondary Objectives

- 1.2.1 To determine the overall response rate to poly-ICLC in the treatment of children with recurrent low grade gliomas; tumor assessments are to be performed per 3D measurements.
- 1.2.2 Progression free survival over the course of the study.
- 1.2.3 Overall survival at 6 months – the time from starting study therapy to death from any cause.
- 1.2.4 To assess the toxicity associated with treatment with poly-ICLC in pediatric patients with recurrent low grade gliomas.
- 1.2.5 To study the effect of treatment with poly-ICLC on the signaling pathways controlling apoptosis in low grade glioma tumor cells.
- 1.2.6 To determine if surrogate markers of tumor response and progression can be identified in the serum, PBMC and/or cerebrospinal fluid of patients with recurrent low grade gliomas treated with poly-ICLC. Proteomics analysis will be performed to obtain protein levels of these markers such as OAS, interferon α , β , γ , PKR kinase, phosphorylation state of eIF2a, and induction of p21^{waf-1}.

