5.0 Required Observations

All Pre-study Observations must be done within 14 days of study entry.

Observation	Pre-Study	Day 1 of Cycle 1	Day 15 of Cycle 1	Prior to subsequent cycles 2-12	Prior to subsequent cycles 13-24	End of therapy/Off Study
History, VS, Physical	x	x	x	x	x	x
Performance Status ¹	x	x	x	x	x	x
Toxicity Evaluation			x	x	x	x
Neuro Evaluation	x	x	x	x	x	x
Concomitant Meds	x	x	x	x	x	x
CBCD, Platelets	x	x	x	x	x	x
PT/PTT	x	x	x	x†	x†	x†
CMP w/Phos	x	x	x	x	x	x
Urinalysis ³	x					
Serum Pregnancy ³	x					
MRI-Brain/Spine**	x			Every 3 cycles starting with end of Cycle 3↑	End of Cycle 18 and 24 only†	x
LP/CSF cytology*	x			Every 3 cycles starting with end of Cycle 3 ²	End of Cycle 18 and 24 only ²	x ²
Biology-red & purple top blood samples		x	x			
Data Collection Submission ⁴	x			x	x	x

1:Performance Status=Karnofsky if > 16 y/o or Lansky if ≤ 16 y/o

2: repeat only if cytopathology showed tumor cells at study entry or disease progression

3: Repeat as needed for good clinical care

4: Data Collection should be submitted monthly

†: Repeat PT/PTT only if abnormal after Day 15

↑ Repeat MRI Spine only if not normal pre study

* Lumbar Puncture/CSF cytology is not required if already done within 4 weeks of study entry.

CSF will be obtained prior to initiation of therapy with Poly ICLC. If positive, CSF will be obtained at 3, 6, 9, 12, 18, 24 months after study entry, as well as the time end of therapy/off study.

MRI Brain/Spine should be obtained with and without gadolinium including pre T1, post T1, T2 and flair sequences. Both axial and either coronal or sagittal pre-post gadolinium images should be obtained.

MRI will be assessed at 3, 6, 9, 12, 18, 24 months after starting the therapy (at the end of those cycles), as well as at the time end of therapy/off study or if subject is going off study prematurely.

**MRI spine does not have to be repeated during the study if it was normal pre-study. It should be repeated at the time end of therapy/off study or if subject is going off study prematurely.

A copy of the MRI images on a CD should be sent to the coordinating site.

5.1: Pretreatment Evaluation (must be performed within 14 days of study entry)

- A. History, vital signs and physical examination, including neurologic evaluation and concomitant medication list
- B. CBC, differential, platelet count, PT/PTT
- C. AST, ALT, alkaline phosphatase, albumin, calcium, phosphorus, total bilirubin
- D. BUN, Cr, urinalysis

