- E. Disease evaluation with either MRI of brain/spine and CSF cytology. (LP is not required if already done within 4 weeks of study entry).
- F. Serum B-HCG in females of childbearing age
- G. Lansky Play Scale assessment for patients ≤ 16 years of age; Karnofsky score for patients >16 years old. (see Appendix I).
- H. Study entry form/eligibility check list to be filled out prior to starting treatment.

5.2: Evaluation during treatment

- A. Disease evaluation (including MRI), if positive at study entry, every 3 cycles for the first 12 cycles (to be done at the end of the cycle), then every 6 cycles for as long as the subject remains on study. MRI spine does not have to be repeated if it was normal pre-study. Disease status and events form is to be filled every 3 months for the first 12 months and then every 6 months while subject is on study.
- B. History, vital signs, physical examination and concomitant medication list at day 1 and day 15 of cycle 1, and then prior to each cycle (monthly for as long as the patient remains on study).
- C. Labs are to be obtained at day 1 and day 15 of cycle 1, and then prior to each cycle (monthly for as long as the subject remains on study).
 - CBC/differential, platelets
 - Chemistry panel including: AST, ALT, alkaline phosphatase, albumin, calcium, phosphorus, total bilirubin, BUN, Cr
 - PT/PTT at Cycle 1 Day 1 and 15, repeat further only if abnormal
- D. Neurologic assessment at each visit with scoring of overall exam compared to previous exam as follows: No change from previous exam; worsening from previous exam; improvement from previous exam.
- E. Record at each visit if steroids are being given and if dose is same, lower, higher than at previous visit. MRI required if steroid dose increased.
- F. Toxicity monitoring form and Lansky Play Scale assessment for subjects ≤ 16 years of age; Karnofsky score for subjects >16 years old. (see Appendix I) at week 2 and then prior to each cycle.

5.3: Evaluation at the end of therapy or relapsed disease

- A. Disease evaluation (including MRI brain and spine) and lumbar puncture for CSF cytology (required only at time of disease progression) with all studies that were initially positive at study entry
- B. History, vital signs, physical examination, and concomitant medication list
- C. Labs:
 - CBC/differential, platelets
 - Chemistry panel including AST, ALT, alkaline phosphatase, albumin, calcium, phosphorus, total bilirubin, BUN, Cr
 - PT/PTT, if still abnormal

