Peripheral mononuclear cells will also be studied by Fluorescence Activated Cell Sorting to establish an immunophenotypic profile for each sample pre and post treatment with poly-ICLC. Regulatory T cells (Tregs), dendritic cells, mononuclear cells, macrophages, B/T cell subtypes, and pro-anti-inflammatory cytokines can also be analyzed. This will also be tested to determine if these markers can serve as feasible additional biomarkers of disease and response.

2. CSF Specimens (optional)

CSF will be obtained prior to initiation of therapy with Poly ICLC. CSF will be obtained via lumbar puncture as part of clinical staging prior to study enrollment, if not already done within 4 weeks of study entry. CSF cytology will be evaluated for presence of tumor cells by an institutional pathologist using standard methods. Approximately 3 ml of CSF will be requested for proteomic analysis. The CSF will be spun at 400-500 g for 10 minutes to remove cellular contaminants. The first 2 ml of CSF supernatant will be aliquoted into four .500 ml units and frozen at -20 to -80 degrees Celsius to be used for proteomic analysis. Each tube must be labeled with the subject's research identifier, the sample type and the time it was drawn.

The remaining 1 ml of CSF will be aliquoted in 0.2 ml units and frozen at -20 to -80 degrees Celsius to be evaluated for cytokines. Each tube must be labeled with the subject's research identifier, the sample type, site from where the sample was obtained, and the time it was drawn.

All blood and CSF biologic samples should be sent on dry ice, along with a completed biologic specimen transmittal form to [name] laboratory located at the Moores Cancer Center at UCSD. Enrolling practitioners should contact [name] at [contact] to notify him of specimens ready for shipment or pickup and delivery:

[name] PhD
Moores UCSD Cancer Center RM 3312
[name]
University of California, San Diego
La Jolla, CA 92093-0819
[contact]
[contact]

Samples will only be received Monday through Thursday.

B. Laboratory analysis

1. Proteomic Biomarker Evaluation

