- Association of baseline levels of proteins (such as OAS, interferon, PKR, phosphorylation state of eIF2a, p21^{waf-1}) in serum, PBMC and/or cerebrospinal fluid with progression free survival.
- Association of changes in levels of proteins (such as OAS, interferon, PKR, phosphorylation state of eIF2a, p21^{waf-1}) serum, PBMC and/or cerebrospinal fluid from baseline with tumor response status at 6 months after treatment with Poly-ICLC.
- Association of changes in levels of proteins (such as OAS, interferon, PKR, phosphorylation state of eIF2a, p21^{waf-1}) in serum, PBMC and/or cerebrospinal fluid from baseline with progression free survival.

9.1: Study Design and Justification of Sample size

9.1.1 This is a single arm study, to determine the radiographic progression free survival (PFS) rate to poly-ICLC in the treatment of children with recurrent or progressive low grade gliomas. The primary endpoint is the progression free survival status at 6 months (PFS6) after starting therapy. The tumor response categories will include complete response, partial response, stable disease or progressive disease, as assessed according to section 7.1.2.

Simon's optimal two-stage design will be used for this study (Simon, 1989). Suppose 50% is the uninteresting level, i.e., if the PFS6 rate is $\leq 50\%$, we will consider the new regimen as not promising. This 50% baseline response rate in the absence of treatment is from historical experience (this rate was also used by the Everolimus study which is a phase II study for recurrent or progressive LLG in children), also taking into account that this study patient population are more refractory. We will test the null hypothesis $H_0: p \leq 50\%$ against the alternative hypothesis $H_1: p > 75\%$, where p is the PFS6 rate. The two stage design proposed below will have 80% power to reject the null and conclude that the true response rate is above 50%, if the true response rate is $\geq 75\%$, at 5% significance level.

The study design can be described in detail as follows:

Stage 1: Fourteen subjects will be accrued; accrual will be held up until the PFS6 results for all the 14 subjects are known. The trial will be terminated at Stage 1 if ≤ 7 subjects have a PFS6 response; otherwise it continues to Stage 2. Note that any subject who goes off study early due to toxicity, will be counted as a non-response (an intent to treat analysis).

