9.1.6 Accrual and study duration

All the 23 patients are expected to be accrued in 3 years and the total study duration will be about 5 to 5.5 years.

9.2: Analysis of Results

9.2.1: Analysis of anti-tumor activity

The "best response" rate is defined as the percent of evaluable subjects who experience a CR or PR or SD (see Section 7.1.2). The best response rates as well as overall response rates at 6 and 24 months will be estimated and exact lower one sided confidence intervals for the true response rates will be presented (Jung, 2004). The duration of response for each subject that has tumor response will be summarized in a table. The same analysis will be done for the tumor response rate based on 3 dimension measurements as in section 7.1.3.

9.2.2: Summary of toxicities and side effects

All observed toxicities and side effects will be recorded on toxicity sheets and the data collection forms. Toxicity information including type, severity, time of onset and resolution, and probable association with the study drugs will be recorded. Toxicities will also be analyzed by NF1 status (NF1 vs. non NF1 subject cohorts). Tables will be constructed to summarize the observed incidence by type of toxicity and severity.

9.2.3: Analysis of Survival

Overall survival and progression-free survival rates will be estimated using the Kaplan-Meier method (Kaplan, 1958).

9.2.4: Analysis of biochemical measures.

Laboratory studies will be done on subject's serum and peripheral blood drawn prior to and at two weeks after starting treatment with Poly ICLC. Levels and changes in the measurement of serum markers and proteins such as OAS, interferon α , β , γ , PKR kinase, eIF2a, and p21^{Waf-1} will be determined via proteomic analysis. For each marker, a Fisher's exact test or a Wilcoxon rank sum test will be used to assess the association of a baseline protein level or changes from baseline against tumor response status at 6 months. A log rank test will be used if the outcome is progression free survival.

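### Change in CSF proteins is listed as a tested endpoint, but cytology-negative children who do not progress have no scheduled second CSF sample

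*Combined protocol and SAP*

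**What the plan says.** **Endpoints.** Section 9.0c ends with four biomarker endpoints: two use baseline levels and two use changes from baseline. The change endpoints are changes in "serum, PBMC and/or cerebrospinal fluid from baseline with tumor response status at 6 months after treatment with Poly-ICLC" and changes "in serum, PBMC and/or cerebrospinal fluid from baseline with progression free survival".

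**Tests.** Section 9.2.4 assigns Fisher's exact or Wilcoxon rank-sum tests to 6-month response and a log-rank test to PFS, with Benjamini-Hochberg control at 0.05. It describes the material as serum and peripheral blood "drawn prior to and at two weeks after starting treatment with Poly ICLC".

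**CSF sampling.** Footnote 2 to the section 5.0 table says of lumbar puncture and cytology: "repeat only if cytopathology showed tumor cells at study entry or disease progression". The notes below the table add: "If positive, CSF will be obtained at 3, 6, 9, 12, 18, 24 months after study entry", and again at end of therapy or off study. Section 5.3A lists, at end of therapy or relapse, "lumbar puncture for CSF cytology (required only at time of disease progression". Section 5.4A(2) makes the CSF research specimen optional and gives it one scheduled time: "CSF will be obtained prior to initiation of therapy with Poly ICLC". The closing paragraph of section 5.5 allows CSF or tissue to be taken at relapse, or when a further operation or lumbar puncture is needed on study. Section 5.4B(3) makes the spinal fluid assays wait for outside funding.

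**Tumor cells.** Objective 1.2.5 is: "To study the effect of treatment with poly-ICLC on the signaling pathways controlling apoptosis in low grade glioma tumor cells". The tissue in section 5.5 is optional and comes from a resection before study entry. Section 9.2.4 plans paired t-tests of change in pathway proteins and expects them to help explain how the drug limits tumor growth.

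**The concern.** A change score needs two samples. For CSF, whether the second exists depends, in cytology-negative children, on whether the tumor has progressed. Response and PFS are the outcomes against which the change is to be tested. A comparison built that way sets children sampled because they progressed against few or no comparable children who did not.

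For PFS there is a further difficulty. A progression-triggered CSF change is measured at the event itself, so it cannot act as an earlier marker of that event, and section 9.2.4 sets no landmark time.

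At stake is an exploratory biomarker claim. A protein that rises in CSF because tumor is advancing could be reported as a marker of sensitivity to poly-ICLC. Likewise, a paired test in blood cells could be reported as an effect in tumor cells. No primary, safety or stopping decision depends on either.

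**Working it through.** **1. The plan's own figures.** No sample size is stated for the biomarker endpoints, so the starting point is the 23 subjects of section 9.1.1. With 14 then 9 subjects, stopping at 7 or fewer and rejecting the therapy at 15 or fewer:

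- Early stopping at p = 0.50: P(X₁ ≤ 7 | 14) = 0.605 (stated 61%).
- Probability of declaring success: Σ over x = 8 to 14 of P(X₁ = x)·P(X₂ ≥ 16 − x | 9). This is 0.046 at p = 0.50 (stated level 5%) and 0.802 at p = 0.75 (stated power 80%).

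The design reproduces, so N = 23 is a fair basis.

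**2. Who has a scheduled second sample.**

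| Subject | Serum and PBMC | CSF after baseline |
|---|---|---|
| Cytology positive at entry | entry and day 15 | 3, 6, 9, 12, 18, 24 months and end of therapy |
| Cytology negative, progresses | entry and day 15 | at progression |
| Cytology negative, does not progress | entry and day 15 | none scheduled |

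The first row selects on a baseline feature. The outcome dependence lies in the contrast between the second and third rows. Day-15 blood is drawn before the first on-study MRI, at the end of cycle 3, so it is not triggered by outcome.

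**3. How many non-progressors would have a fixed-schedule CSF.** Let q be the cytology-positive rate at entry. The documents admit children with leptomeningeal dissemination but give no rate, so q is assumed to run from 0 to 30% and to be unrelated to outcome. Let p be the 6-month PFS rate, at the null (50%) and target (75%) values. Section 7.1.4 counts stable disease within the overall response rate, so 6-month response is taken here as being progression-free at 6 months.

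- Expected non-progressors with CSF = 23 × p × q
- Chance of none = (1 − p × q)²³

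| q | Expected, p = 50% | Chance of none | Expected, p = 75% | Chance of none |
|---|---|---|---|---|
| 0% | 0 | 1.000 | 0 | 1.000 |
| 5% | 0.58 | 0.559 | 0.86 | 0.415 |
| 10% | 1.15 | 0.307 | 1.73 | 0.166 |
| 20% | 2.30 | 0.089 | 3.45 | 0.024 |
| 30% | 3.45 | 0.024 | 5.2 | 0.003 |

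Progressors with a CSF number at most 23 × (1 − p) = 11.5 at p = 50% and 5.75 at p = 75%. These are ceilings, because the research specimen is optional.

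A cytology-negative child who is progression-free at 6 months and progresses later would give a second sample only then, after the 6-month status is fixed and again because of progression.

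**4. What a test could show.** With a non-progressors and b progressors, the smallest two-sided exact rank-sum p-value is 2/C(a+b, a).

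- a = 1: 2/7 = 0.286 for b = 6; 2/13 = 0.154 for b = 12.
- a = 2: 2/28 = 0.071 for b = 6; 2/91 = 0.022 for b = 12.

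Fisher's test on a dichotomized marker can reach half these values. With one non-progressor that is 1/7 = 0.143 or 1/13 = 0.077, still above 0.05 before any false-discovery adjustment. Had all 23 subjects paired CSF, the floor would be 2/C(23, 6) = 2.0 × 10⁻⁵ for 17 against 6.

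**5. Tumor cells.** Objective 1.2.5 set against sections 5.4 and 5.5: the only before-and-after pairs scheduled in every subject are blood at entry and day 15. Tumor tissue after treatment arises only if an operation happens to be needed.

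**The case against.** The strongest reply is that section 9.2.4, which specifies the tests, already names only serum and peripheral blood at baseline and two weeks. On that reading the CSF change tests would never be run, and the and/or in 9.0c does not require CSF from every child. This is a fair reading, and it shows how small the fix is. But 9.2.4 does not withdraw the CSF change endpoints, and 9.0c calls them specific endpoints, so an analyst following 9.0c could run them.

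The work is also openly exploratory: section 5.4B says so of the proteomics, and section 5.4A already calls the PBMC readout a surrogate. That stands, and it limits the importance of the point.

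A reader might infer several stronger things that the documents do not support:

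- That all the change-from-baseline tests are outcome-selected. The serum and PBMC tests are not.
- That serial CSF in cytology-positive children is outcome-selected. It follows a fixed schedule after a baseline finding; that limits numbers and generalizability but is not selection on outcome.
- That a cytology-negative non-progressor can never have a second CSF. Section 5.5 leaves an unscheduled route. It is not random and does not repair the comparison, but it rules out absolute statements.
- That every progressor will have a research CSF sample. Later punctures are listed for cytology, relapse samples are permitted rather than required, and 5.3A can be read as covering only studies positive at entry.
- That missing tumor tissue is also outcome selection. It is an objective left unmeasured, which is a different fault.

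**Conclusion.** The point holds for the CSF component of the two change endpoints in 9.0c, and as a separate matter for objective 1.2.5. CSF change tests that include progression-triggered samples are conditioned on outcome. Tests confined to fixed-schedule samples would rest on about 0 to 5 non-progressors. With only one, neither named test could reach 0.05 at the group sizes considered.

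The counts depend on the assumed 0–30% positive rate. They also assume that entry cytology is unrelated to outcome (if positive children progress more often, the counts fall) and that the trial reaches 23 subjects. The lack of a scheduled second CSF in cytology-negative non-progressors depends on none of these assumptions. Day-15 serum and PBMC analyses stand as planned. This is a minor, worthwhile correction to wording.

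**What to change.** 1. In 9.0c, limit the two tested change-from-baseline endpoints to serum and PBMC, baseline to day 15, in line with 9.2.4.
2. Keep CSF in the two baseline-association endpoints; this still serves the CSF part of objective 1.2.6.
3. State that CSF obtained because of progression is excluded from the association tests.
4. Report CSF changes descriptively, with fixed-schedule samples from cytology-positive children shown separately from samples at progression.
5. Reword objective 1.2.5 and the pathway conclusion in 9.2.4 to refer to pathway changes in PBMC as a surrogate.

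These are text changes only. They add no procedures and leave the primary endpoint and sample size untouched. The cost is the loss of an exploratory CSF change test, including any test in cytology-positive children alone, which the planned sampling is too thin to support.

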Stage 2: Nine more patients will be accrued. We will reject the therapy if among all the 23 (14+9) subjects, the number of patients who have a defined response is ≤ 15 .

Early stopping probability: Under this design, if the null hypothesis is true, the probability of stopping the trial early will be 61%.

9.1.2 Interim analysis and early stopping for efficacy:

The interim analysis will be conducted as soon as the first 14 patients have accrued and are evaluable for the primary outcome. If ≤ 7 subjects had a defined response, the trial will be stopped early for lack of efficacy.

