9.1.4 Final analysis for the primary endpoint

If the study continues, after all 23 subjects are evaluable for efficacy and safety the study data set will be locked. Out of the total of 23 subjects, if the number of subjects with PFS6 is 16 or more, the conclusion will be that the trial has demonstrated a statistically significant improvement above a 50% PFS6 rate. The final estimated PFS6 rate will also be presented, along with a lower 90% confidence interval.

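### Does labelling the 7/14, 15/23 rule as Simon's optimal design, when it is the minimax design, call for a change?

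*Combined protocol and SAP*

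**What the plan says.** Section 9.1.1 names the method by citation: Simon's "optimal two-stage design will be used for this study". It gives the null rate ("Suppose 50% is the uninteresting level"), sets the alternative at a 6-month progression-free rate of 75%, and says the design "will have 80% power to reject the null" "at 5% significance level".

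The decision rule is then given in numbers. Stage 1 enrols 14 and stops if 7 or fewer succeed. Stage 2 adds nine, with the final cut-off stated as "We will reject the therapy if among all the 23 (14+9) subjects" 15 or fewer succeed. The section adds that under the null "the probability of stopping the trial early will be 61" per cent.

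Section 9.1.2 repeats the interim cut-off of 7 among the first 14. Section 9.1.4 gives the matching success rule, "if the number of subjects with PFS6 is 16 or more" out of 23. Section 9.1.6 plans accrual of 23. The word *minimax* does not appear, and no expected sample size is reported.

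**The concern.** In the usual statistical vocabulary for Simon's designs, *optimal* and *minimax* mean different things. Both meet the same error limits. The optimal design has the smallest expected sample size when the null is true; the minimax design has the smallest maximum sample size. A reader who computes the optimal design from the inputs in section 9.1.1 gets 11 then 25 subjects, with cut-offs 6 and 16, and not 14 then 23 with cut-offs 7 and 15.

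Such a mismatch can be a symptom of something worse. The boundaries might have been copied from a design for other inputs, in which case the stated 5% level or 80% power might not hold. Or one set of numbers might have been intended and another printed, in which case the trial could stop, or declare success, at the wrong count. The early-stopping figure also does not quite reproduce. These possibilities make the label worth checking.

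**Working it through.** **Inputs**, all from sections 9.1.1 and 9.1.4: p0 = 0.50, p1 = 0.75, level 0.05 (one-sided, since the null is a rate of at most 50% against a higher one), power 0.80; printed rule r1/n1 = 7/14, r/n = 15/23.

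**1. Early-stopping probability under the null.** With X ~ Bin(14, 0.5):

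P(X ≤ 7) = (2^14 + C(14,7))/2 ÷ 2^14 = (16384 + 3432)/2 ÷ 16384 = 9908/16384 = 0.6047.

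The plan prints 61%. The exact value rounds to 60%; 61% is what results from rounding to 60.5% and then rounding again. For 6/11 the corresponding figure is (1024 + 462)/2048 = 1486/2048 = 0.7256. The printed figure therefore belongs to the printed boundaries.

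**2. Type I error of the printed rule.** With Y ~ Bin(9, 0.5) for stage 2,

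α = Σ (x = 8 to 14) P(X = x) · P(Y ≥ 16 − x).

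| x | C(14,x) | count for Y ≥ 16 − x (out of 512) | product |
|---|---|---|---|
| 8 | 3003 | 10 | 30030 |
| 9 | 2002 | 46 | 92092 |
| 10 | 1001 | 130 | 130130 |
| 11 | 364 | 256 | 93184 |
| 12 | 91 | 382 | 34762 |
| 13 | 14 | 466 | 6524 |
| 14 | 1 | 502 | 502 |

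The products sum to 387224. Dividing by 16384 × 512 = 8388608 gives α = 0.0462, below 0.05.

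**3. Power.** The same sum with p = 0.75 gives 0.8016, above 0.80. Both stated error rates hold.

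**4. Which design is it?** An exhaustive search over (r1, n1, r, n) with exact binomials, requiring α ≤ 0.05 and power ≥ 0.80, finds no feasible design with maximum n below 23. Among designs with n = 23, the smallest expected size under the null belongs to 7/14, 15/23:

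E0(N) = 14 + 9 × (1 − 0.6047) = 17.56.

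The next is 6/13, 15/23 at 18.00. The printed rule is therefore the minimax design. Over all n (searched to 80), the smallest expected size under the null is at 6/11, 16/25:

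E0(N) = 11 + 14 × (1 − 0.7256) = 14.84, with α = 0.0458 and power 0.8005.

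That is the optimal design. Changing the error limits to 0.025 with 80% power, 0.05 with 90%, or 0.10 with 80% does not make 7/14, 15/23 optimal either.

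**5. The two designs side by side.**

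| | Printed 7/14, 15/23 | Optimal 6/11, 16/25 |
|---|---|---|
| Type I error | 4.6% | 4.6% |
| Power at 75% | 80.2% | 80.1% |
| Maximum N | 23 | 25 |
| Early stop at 50% | 60.5% | 72.6% |
| Expected N at 50% | 17.6 | 14.8 |
| Early stop at 75% | 3.8% | 11.5% |
| Expected N at 75% | 22.7 | 23.4 |

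The last row is 14 + 9 × (1 − 0.0383) = 22.66 and 11 + 14 × (1 − 0.1146) = 23.40.

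**The case for a change.** The case for acting is that a design statement should be reproducible and this one is not. The section names a specific design, and the printed rule lacks its defining property: expected size under the null is 2.7 subjects (17.56 − 14.84), or about 18%, above the minimum. A monitoring-board statistician who recomputes the named design finds a different stage 1 size, final cut-off and maximum. Section 3.1's total of 24 evaluable subjects matches neither 23 nor 25, so it does not settle the matter. Correcting one word would cost almost nothing.

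The factual part of this stands: the label is wrong in the usual sense of the term. A softer reading is possible, because the reference list in section 11.0 shows that the cited paper has *optimal two-stage designs* in its title, so the phrase may name the family of designs. The inputs still show that the member used is the minimax one.

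The claimed harm does not stand. The rule is spelled out as counts wherever it is used, those counts agree with each other, and the printed 61% fits them and rules out 6/11. A reader who notices the mismatch can tell from the document that the numbers are intended and the word is loose. The 2.7-subject gap is one side of a trade-off and not a loss caused by the label; the other side is a smaller maximum and a lower chance of abandoning an active drug at stage 1.

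**Conclusion.** The label in section 9.1.1 is inaccurate, but no change to the plan follows. The printed rule is a valid Simon design that meets the stated 5% level (exact 4.6%) and 80% power (exact 80.2%), with the smallest maximum sample size those limits allow. Stage sizes, the stopping count, the success count and the conclusion drawn from 16 or more of 23 are the same whichever name is used. No printed figure depends on the word *optimal*, since the plan reports no expected sample size.

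The early-stopping figure is about half a percentage point high (61% against 60.47%), a rounding matter in a descriptive number that triggers nothing. Printing exact error rates or the expected size would be a courtesy to readers and would correct no error. Moving to 6/11, 16/25 to match the label would exchange one set of merits for another, with no gain in type I error or power.

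This rests on a one-sided 5% level, which the form of the hypotheses implies, on exact binomial calculation, and on every subject being counted as a success or a failure at 6 months, as section 9.1.5 provides.
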